8.4.9.1.3 Rescue Therapy

If deemed to be medically necessary by the investigator (eg, to control intolerable AD signs/symptoms), rescue therapies can be prescribed to the subjects at any time during the study, except during the run-in period. (Subjects receiving rescue therapies during the run-in period are not eligible to participate in the study.)

As a general guideline and per individual investigator judgment, rescue therapy should not be prescribed within the first 2 weeks after baseline (ie, Week 2) to allow a minimum time for study drug exposure in the presence of background therapy.

Rescue treatments are only treatments that directly treat AD (mainly those that are approved or are standard of care) and include topical and systemic treatments as outlined. Rescue therapies include:

- Higher potency of TCS (equivalent to class I-II according to the US classification)²
- Oral corticosteroids
- Biologics (including their biosimilars)
- Systemic nonsteroidal immunosuppressants/immunomodulators
- Phototherapy

Antihistamines, sleep aids, topical and systemic antibiotics, and anti-itch creams are **not** considered to be rescue therapy because they do not directly treat AD.

Whenever possible, investigators should first use topical medication as rescue therapy before escalating to systemic therapies. If subjects receive topical treatments or phototherapy as rescue therapy, study drug administration should be continued unless there is a safety concern according to the investigator's judgment. If subjects receive systemic rescue therapy, the study drug administration must be permanently discontinued.

CONFIDENTIAL

For the purpose of efficacy analysis, subjects receiving any rescue therapies will be considered as treatment failures (ie, non-responders). Investigator assessments of efficacy should be performed before initiating rescue therapy. Subjects requiring rescue therapy between scheduled visits should return to the clinic (unscheduled visit) for investigator assessment of efficacy before starting rescue therapy. Further, the use of any rescue therapies should be documented in the CRF.

8.4.9.2 Prohibited Medication/Therapy

Treatment with the following concomitant medications/therapies is prohibited during the study unless otherwise specified in Table 10. “As needed” (PRN) use of TCS or TCI is not permitted.

Table 10: Prohibited Medication/Therapy

Treatment(s)	Timeframe	
	Before Baseline/Day 1	Day 1 – Week 56
Coal tar products	2 weeks	Prohibited
Topical PDE-4 inhibitor	2 weeks	Prohibited
Non-authorized medium- or low-potency TCS	2 weeks	Prohibited
Higher-potency TCS (US classification I-II or equivalents) ²	2 weeks	Prohibited*
Topical medications, including authorized TCS/TCI, with occlusive dressings (eg, wet wraps)	2 weeks	Prohibited
Systemic corticosteroids (corticosteroid inhalers are permitted)	4 weeks	Prohibited*
Phototherapy	4 weeks	Prohibited*
Tanning bed use	4 weeks	Prohibited
Immunosuppressive or immunomodulatory drugs (eg, cyclosporine A, oral tacrolimus, cyclophosphamide, azathioprine, methotrexate, mycophenolate mofetil, Janus kinase inhibitors)	4 weeks or 5 half-lives (whichever is longer)	Prohibited*
Biologics and their biosimilars (eg, etanercept, adalimumab, infliximab, omalizumab, etc)	8 weeks or 5 half-lives (whichever is longer)	Prohibited*
Dupilumab	10 weeks	Prohibited*

CONFIDENTIAL

Treatment(s)	Timeframe	
	Before Baseline/Day 1	Day 1 – Week 56
Live attenuated vaccine	12 weeks	Prohibited
Drugs with a sedative effect such as benzodiazepines, imidazopyridines, barbiturates, sedative anti-depressants (eg, amitriptyline), SSRIs (eg, paroxetine), or SNRIs, except if these treatments were taken at a stable dose for at least 3 months before screening (Stable treatment with antihistamines with sedative effect is allowed at a dose that, based on previous experience, is well tolerated by the subject.)	1 week	Prohibited
Gabapentinoids (eg, gabapentin, pregabalin)	4 weeks	Prohibited
Cannabinoids	2 weeks	Prohibited
Alternative medicine for AD (eg, traditional Chinese medicine)	2 weeks	Prohibited

Abbreviation(s): AD=atopic dermatitis; PDE-4=phosphodiesterase-4; SNRI= serotonin-norepinephrine reuptake inhibitor; SSRI=selective serotonin reuptake inhibitor; TCI=topical calcineurin inhibitor; TCS=topical corticosteroid; US=United States.

Note:

Subjects should not interrupt ongoing treatment with medications important for the subject's health for the sole purpose of participating in this study.

* Unless used as rescue therapy during the study.

If a prohibited therapy becomes necessary for the safety of the subject, the investigator should notify the medical monitor and discuss possible alternatives. If a subject receives a prohibited therapy during the clinical study (eg, inadvertent short-term use), the investigator should also notify the medical monitor and discuss whether or not it is acceptable for the subject to continue receiving the study drug.

Specifically, the use of systemic corticosteroids during the study is prohibited except when used as rescue therapy for AD (in accordance with the instructions in Section 8.4.9.1.3). If the use of systemic corticosteroids becomes necessary for the safety of the subject to treat conditions other than AD, the study drug should be temporarily discontinued for the duration of treatment with systemic corticosteroids plus 5 half-lives.

Immunization with non-live COVID-19 vaccine is permitted during the study if in accordance with local regulations. Wherever possible, it is recommended to avoid

CONFIDENTIAL

administration of COVID-19 vaccinations within 1 week of study drug dosing. A different anatomical location should be used for study drug administration and vaccine administration.

8.4.10 Product Technical Complaints

All DCS units must be inspected prior to preparation/injection by the persons performing the preparation/injection to ensure absence of visual defects that could lead to a DCS PTC. This also includes the needle and plunger rod. In case of doubt, the DCS should not be used, and the deficiency must be reported as defined in the pharmacy manual.

All PTCs should be reported to the sponsor/designee by filing the relevant forms available in the Investigator Site File and the pharmacy manual and as required by local regulations. A PTC is any written, electronic, or oral communication that alleges deficiencies related to the identity, quality, reliability, safety, durability, effectiveness, or performance of a drug or delivery system. Examples may include but are not limited to appearance issues, discoloration, odor, broken/cracked syringe, missing parts, damaged stoppers, and foreign matter in lyophilized powder or diluent. These complaints may or may not represent a potential risk to the subject. For these types of events, a form must be completed as per the specific instruction by the site personnel, pictures of the defective DCS must be attached, and forwarded to the sponsor/designee at the latest on the next working day. Reporting to health authorities will be in accordance with local regulations. The defective DCS/items must be kept in case of investigation need as defined in the pharmacy manual and may be requested to be sent to the Sponsor/designee in accordance with regulations.

Refer to the current version of the pharmacy manual for further details.

8.5 Duration of Subject Participation

The expected duration for each subject's participation in the study depends on the clinical response and may be:

- Up to 28 weeks (including a 4-week screening period, a 16-week initial treatment period, and an 8-week follow-up period [12-weeks after the last study medication injection]) for subjects who are non-responders at the completion of the initial treatment period (Week 16)

CONFIDENTIAL

- Up to 60 weeks (including a 4-week screening period, a 16-week initial treatment period, a 32-week maintenance period, and an 8-week follow-up period [12-weeks after the last study medication injection]) in subjects who are clinical responders at the completion of the initial treatment period (Week 16)

The 12-week follow-up visit is not required for subjects who will continue in the LTE study (Protocol 118163).

8.5.1 Early Termination Visit

Subjects may discontinue from the study or discontinue the study treatment only and continue to participate in the study.

Subjects who prematurely discontinue from the study should undergo final study assessments according to the following guidelines:

- Subjects discontinued from the study during the initial treatment period on/before the Week 16 visit should attend an ET visit. A follow-up/final visit is required 12 weeks after the last study drug administration.
- Subjects discontinued from the study during the maintenance period should attend an ET visit.

A follow-up/final visit is required 12 weeks after the last study drug administration.

Subjects who prematurely discontinue the study drug will be asked to continue participation in the study and return for all remaining visits and assessments (including daily assessment of pruritus, sleep disturbance, etc). Participation will continue until the subject completes the final study visit or otherwise discontinues study participation.

Subjects requiring rescue medication (with or without study medication discontinuation) may be eligible for LTE study participation:

- Subjects requiring rescue medication during the initial treatment period should continue with study visits including the Visit 6/Week 16. A follow-up/final visit is not required for subjects participating in the LTE study.
- During the maintenance period, for subjects requiring rescue medication before the Week 32 visit, a wait period with continuing study visits until the Week 32 visit is due is required. Thereafter, no wait period is required. Subjects must complete the final study/ET assessments prior to rollover to the LTE study.

A follow-up visit is not required for subjects who will participate in the LTE.

CONFIDENTIAL

8.5.2 Unscheduled Visit

The subject should be reminded to adhere to the study schedule. Unscheduled visits are defined as visits to repeat testing for abnormal laboratory results, for follow-up of AEs, or to conduct efficacy assessments for subjects requiring rescue medication between regularly scheduled study visits. Visits occurring outside of the visit window are not considered unscheduled visits.

Assessments to be conducted at the unscheduled visit will depend on the reason for the visit: Any of the procedures/assessments listed in Section 8.1.2 may be conducted, but not all are required. Blood sample collection for PK and ADA analyses are only required during unscheduled visits that are conducted for safety reasons.

CONFIDENTIAL

9 STUDY ASSESSMENTS

A written, signed ICF, assent form, and Health Insurance Portability and Accountability Act (HIPAA) authorization is required before any study-related procedures are performed.

Upon provision of the signed ICF/assent form, each subject will be assigned a unique SIN. For the duration of the entire clinical study, the subject will be identified using the SIN in all documentations and discussion.

The planned study assessments are in Section 8.1.2 . At each visit, assessments/procedures should be performed in the following order:

1. Patient-reported efficacy and safety measurements
2. Investigator assessments (including efficacy and safety)
 - ECG should be done before vital signs measurements (and blood draws).
See Section 9.2.10
3. Sample collections for laboratory assessments
4. Sample collections for correlative assessments (PK, ADA, PD, and optional PGx)
5. Administration of study drug injections

9.1 Efficacy Assessments

Efficacy measurements should be conducted by the investigators (or trained designees) and subjects (for patient-reported efficacy measurements) according to Section 8.1.2 . Whenever possible, the same evaluator should make the assessment throughout the study. Refer to Section 7.2 and Section 7.3 for efficacy endpoints.

9.1.1 Investigator's Global Assessment

The IGA is a 5-point scale ranging from 0 (clear) to 4 (severe) used by the investigator or trained designee to evaluate the global severity of AD and the clinical response to a treatment. Treatment success is defined as 0 (clear) or 1 (almost clear) and a 2-point improvement from baseline (see Appendix 4).³⁵

9.1.2 Eczema Area and Severity Index

The EASI is a validated measure commonly used in clinical trials and clinical practice to assess the severity and the extent of AD signs. The EASI score is a composite score

CONFIDENTIAL

ranging from 0 to 72 (see [Appendix 5](#)).³⁶ The severity of erythema, induration/papulation, excoriation, and lichenification will be assessed by the investigator or trained designee on a scale of 0 (absent) to 3 (severe) for each of the 4 body areas: head/neck, trunk, upper limbs, and lower limbs, with half points allowed. In addition, the extent of AD involvement in each of the 4 body areas will be assessed as a percentage by body area of head, trunk, upper limbs, and lower limbs, and converted to a score of 0 to 6. The EASI score will be calculated in the CRF.

9.1.3 Pruritus Numeric Rating Scale

The Pruritus NRS is a scale to be used by the subjects to report the intensity of their pruritus (itch) during the last 24 hours (see [Appendix 6](#)). Two measures of Pruritus NRS will be assessed (average and peak/maximum itch intensity). The PP NRS has been validated in other AD clinical trials in adults, and the minimum clinically important difference was shown to be 4.²⁵

The average pruritus NRS (AP NRS) provides a measure of overall pruritus intensity over a given period and has clinical relevance to both subjects and physicians because peak pruritus may show higher intensity but short duration.

Subjects will be asked the following questions:

- For average itch intensity (AP NRS): “On a scale of 0 to 10, with 0 being ‘no itch’ and 10 being the ‘worst itch imaginable’, how would you rate your itch overall during the previous 24 hours?”
- For maximum itch intensity (PP NRS): “On a scale of 0 to 10, with 0 being ‘no itch’ and 10 being the ‘worst itch imaginable’, how would you rate your itch at the worst moment during the previous 24 hours?”

The screening PP NRS will be determined by a single assessment using the PP NRS (score ranging from 0 to 10) for the 24-hour period immediately preceding the screening visit. The baseline PP NRS will be determined based on the average of daily PP NRS (score ranging from 0 to 10) during the 7 days immediately preceding baseline (rounding to nearest whole number is not permitted). A minimum of 4 daily scores out of the 7 days immediately preceding baseline is required for this calculation. Subjects will receive instructions on how to record their pruritus NRS scores and will complete the assessment once daily in the evening throughout the clinical study (including the run-in and the follow-up period).

CONFIDENTIAL

The proportion of “itch-free days” will be calculated from the number of subject-reported PP NRS and AP NRS scores of 0 or 1 during the treatment period.

9.1.4 Sleep Disturbance Numeric Rating Scale

The SD NRS is a scale to be used by the subjects to report the degree of their sleep loss related to AD (see [Appendix 7](#)). Subjects will receive instructions on how to record their SD NRS scores and will complete the assessment once daily in the morning throughout the clinical study (including the run-in and the follow-up period).

Subjects will be asked the following question:

- “On a scale of 0 to 10, with 0 being ‘no sleep loss related to the symptoms of atopic dermatitis’ and 10 being ‘I did not sleep at all due to the symptoms of atopic dermatitis’, how would you rate your sleep last night?”

CCI [REDACTED]

[REDACTED]

[REDACTED]

[REDACTED]

[REDACTED]

[REDACTED]

CCI [REDACTED]

CCI [Redacted]

[Redacted]

[Redacted]

[Redacted]

[Redacted]

[Redacted]

[Redacted]

9.1.9 Application of Topical Medication for Atopic Dermatitis

Subjects will be instructed to use the authorized background topical therapy as prescribed by the investigator. Each evening, subjects will be asked to record the response (yes/no) to the following question, “Did you apply the atopic dermatitis medication your doctor gave you to your skin today?” throughout the clinical study (including the run-in and the follow-up period).

9.2 Safety Assessments

Safety assessments will be conducted for all subjects at the screening visit (upon signing of the ICF) and at every subsequent visit.

CONFIDENTIAL

9.2.1 Adverse Events

Adverse Event Definition

An AE is defined as any untoward medical occurrence in a clinical study subject administered a medicinal product which does not necessarily have a causal relationship with this treatment. An AE can therefore be any unfavorable and unintended sign (including an abnormal laboratory finding), symptom, or disease temporally associated with the use of a medicinal (investigational) product, whether or not it is related to the medicinal (investigational) product. This includes an exacerbation of pre-existing conditions or events, intercurrent illnesses, drug interaction, or the significant worsening of the indication under investigation that is not recorded elsewhere in the CRF under specific efficacy assessments.

Note(s):

- Any new sign or symptom reported by the subject that appears after accidental or intentional overdose or misuse should be reported as an AE.
- Whenever possible, a diagnosis should be reported on the AE form, instead of signs, symptoms, or abnormal laboratory values.
- Pregnancy is not to be considered an AE; however, it must be monitored and reported as described in Section 9.2.1.5.
- Each worsening of a chronic disease from the screening visit should be reported as a new AE.

The investigator or designee will report all AEs that occur from the time the ICF is signed until the end of the study. The sponsor/CRO should be informed if the investigator becomes aware of any safety information that appears to be drug related, even after the subject has completed the clinical study.

At each post-enrollment visit, the investigator (or sub-investigator) will question the subject about AEs using an open non-persuasive question to elicit reporting of AEs (for example, "Have you noticed any change in your health since the last visit?"). Directed questioning and examination will then be performed as appropriate.

During optional subjects interviews, the subject will be queried on changes in his or her condition and perceived effects of the study treatment. Any unfavorable changes reported by the subjects will be reported to the Investigator or designee by the designated CRO responsible for the interviews. The Investigator will be responsible for reporting all AEs,

CONFIDENTIAL

including those reported during the interviews following the process described in the protocol.

Any AE occurring during the AE reporting period, whether it is related to the study drug(s) or not, will be recorded immediately in the source document and described on the Adverse Event Form (“AE Form”) along with the date of onset, severity, relationship to the study drug(s), and outcome, without omitting any requested and known information. Additional information will be requested under certain circumstances.

Adverse events assessed as related to the treatment or study procedure will be monitored until they have resolved or reached a stable condition. Other AEs will be monitored until the last visit if they have not resolved or reached a stable condition.

The investigator will obtain and maintain in the subject’s files all pertinent medical records, information and medical judgment from colleagues who assisted in the treatment and follow-up of the subject. If necessary, the investigator will contact the subject’s personal physician or hospital staff to obtain further details.

Assessment of Severity

Each AE will be assigned a category by the investigator as follows:

- Mild: An AE that is easily tolerated by the subject, causes minimal discomfort, and does not interfere with everyday activities.
- Moderate: An AE that is sufficiently discomforting to interfere with normal everyday activities; intervention may be needed.
- Severe: An AE that prevents normal everyday activities; treatment or other intervention usually needed.

If there is a change in severity of an AE, it must be recorded as a separate event.

Assessment of Causality

The investigator is to determine whether there is a reasonable causal relationship between the occurrence of the AE, and exposure to the study drug (ie, nemolizumab or placebo) and/or study procedure (eg, injection, topical background therapy, blood sample collection). Medical judgment should be used to determine the relationship, considering all relevant factors including the pattern of the reaction, temporal relationships, relevant medical history, and confounding factors such as co-medication or concurrent diseases.

CONFIDENTIAL

The expression “reasonable causal relationship” is meant to convey in general that there are facts or arguments to suggest a causal relationship (ICH E2A, Section IIIA 1).

The relationship assessment for an AE is to be completed using the following definitions as a guideline for all AEs occurring during this clinical study:

Reasonable possibility:

According to the reporting investigator, there is a reasonable possibility (ie, suggestive evidence or arguments) that there is a causal relationship irrespective of the dose administered:

- Between the study drug (nemolizumab) and the AE, and/or
- Between the clinical study protocol procedure (eg, injection, topical background therapy, blood sample collection) and the AE

No Reasonable Possibility:

No suggestive evidence or arguments can be identified regarding a causal relationship between the study drug or the clinical study protocol procedure and the AE.

Action Taken

The investigator will describe the action taken in the appropriate section of the CRF, as follows:

- None
- Study drug stopped
- Study drug temporarily interrupted
- Concomitant medication (any additions or discontinuations)
- Other, specify

Follow-up of Adverse Events

All investigators should follow-up with subjects with AEs until the event is resolved or until, in the opinion of the investigator, the event is stabilized or determined to be chronic. Details of AE resolution must be documented in the CRF.

CONFIDENTIAL

Subjects should be followed up for 12 weeks (\pm 5 days) after receiving the last dose of study drug, and any AEs that occur during this time should be reported according to the procedures outlined above.

Documentation and Reporting of Adverse Events

Adverse events should be reported and documented in accordance with the procedures outlined below. All AEs occurring during the study must be documented on the relevant CRF pages. The following data should be documented for each AE:

- Description of the symptom event
- Classification of “serious” or “not serious”
- Severity
- Date of first occurrence and date of resolution (if applicable)
- Action taken
- Causal relationship
- Outcome of event (unknown, recovered, not yet recovered, recovered with sequelae, death [with date and cause reported])

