10.1.4.2 Adverse Events

Treatment-emergent AEs, defined as those AEs occurring after the first administration of study treatment until the last study visit, will be tabulated in frequency tables by system organ class and preferred term based on the Medical Dictionary for Regulatory Activities for each study phase. Additional summary tables will be provided for SAEs, AEs related to the study drug(s) (reasonable possibility, no reasonable possibility), AEs related to the study procedure, AESIs, and AEs leading to treatment discontinuation and study withdrawal. For a given AE, a subject will be counted once even if he/she has experienced multiple episodes of that particular AE.

Pretreatment AEs will be listed separately.

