- The month and year are reported: If the subject received the first study drug in the month and year reported, then the date of the first dose of study drug will be used as the start date; otherwise, the first day of the month and year will be used as the start date.

This document is confidential.

- The time is collected but missing: If the start date is the same as the date the subject started receiving study drug, then the time of the first dose of study drug will be used as the start time; otherwise, 00:00 will be used as the start time.

For the end of a concomitant medication/procedure or AE:

- Only the year is reported: The earlier between December 31 of the year reported and the date of the last study contact with the subject will be used as the stop date.
- The month and year are reported: The earlier between the last date of the month and year reported and the date of the final contact with the subject will be used as the stop date.
- The time is collected but missing: 23:59 (or 23:59:59 if collected up to seconds) will be used as the stop time.

If an AE has the start date completely missing and the stop date on/after the first dose date of study drug, this AE will be considered as treatment emergent (TEAE).

If a medication/procedure has the stop date completely missing, this medication/procedure will be considered as ongoing and concomitant. If the start date of a medication/procedure is completely missing and impossible to identify different by stop date, this medication will be considered as concomitant.

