13.1. Adverse Events

Adverse events (AEs) will be coded using MedDRA Version 25.0, March 2022.

Treatment-emergent AEs, defined as those AEs occurring after the first administration of study treatment until end of study, will be tabulated in frequency tables by System Organ Class (SOC) and Preferred Term (PT) based on the Medical Dictionary for Regulatory Activities for each study period (Initial Period, Maintenance Period, and Follow-up Period). Missing date information will be handled using the algorithm described in Section 8.3.

Additional summary tables by SOC and PT will be provided for SAEs, AEs related to the study drug(s), AEs related to the study procedure, adverse events of special interest (AESIs), and AEs leading to treatment discontinuation and study withdrawal.

AEs will be summarized using the number and percent of subjects reporting each SOC and PT and sorted alphabetically by SOC and by descending frequency of PT within SOC.

Subjects who experienced multiple events within the same SOC will be counted once in the SOC summary. When summarizing by causality or maximum severity, if a subject experiences more than 1 occurrence of the same AE, the occurrence with the greatest severity and the closest association with the study drug will be used in summary tables. For summary by maximum severity, subjects who experience multiple occurrence of an AE, the most severe category for each SOC and for each PT within each SOC will be considered in the summary.

TEAEs related to study drug/study procedure are those that are identified as reasonable possibility.

If relationship or severity is missing, the event will be considered as AE related to study drug/study procedure or severe AE.

An AESI is a noteworthy treatment-emergent event for the study drug that should be monitored closely and reported promptly. An AESI can be either serious or non-serious. Based on the potential risks of nemolizumab and the risks associated with biologics in general (i.e., class effects), the following AEs will be considered as AESIs: Injection-related reactions, Newly diagnosed asthma or worsening of asthma, Infections, Peripheral edema:limbs, bilateral, Facial edema and elevated ALT or AST (>3xULN) in combination with elevated Bilirubin (>2xULN).

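### Partial AE start dates are set to first dose without checking a known stop date, and severity-change records have neither a dating rule nor a worsening rule for the TEAE tables

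*Protocol*

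**What the plan says.** **Collection.** Protocol 9.2.1: "The investigator or designee will report all AEs that occur from the time the ICF is signed until the end of the study". Events from screening and run-in are therefore in the database. Each is recorded "along with the date of onset, severity, relationship to the study drug(s), and outcome". The list of items to document later in the same section asks instead for "Date of first occurrence and date of resolution (if applicable").

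**Severity changes.** Protocol 9.2.1: "If there is a change in severity of an AE, it must be recorded as a separate event". No direction is given. For chronic disease the same section is directional: "Each worsening of a chronic disease from the screening visit should be reported as a new AE".

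**TEAE definition.** Protocol 10.1.4.2: "Treatment-emergent AEs, defined as those AEs occurring after the first administration of study treatment until the last study visit". SAP 13.1: "Treatment-emergent AEs, defined as those AEs occurring after the first administration of study treatment until end of study". Neither compares severity with an earlier level. SAP 13.1 tabulates by Initial, Maintenance and Follow-up Period but does not say how an event is assigned to a period.

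**Partial start dates.** SAP 8.3, for a start known by month and year: "If the subject received the first study drug in the month and year reported, then the date of the first dose of study drug" becomes the start; otherwise the first of that month is used. A start known only by year is treated in the same way. The stop date decides emergence only when the start is completely missing.

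**The concern.** The partial-date rule can contradict data already in hand. If the stop date shows that the event was over before first dose, the imputed start falls after the stop and a pre-treatment event enters the TEAE tables. The SAP does use stop dates elsewhere. Sections 9.4 and 9.5 class a procedure or medication with a partial stop date as concomitant unless the known part of that date shows that it ended before first treatment. Adverse events have no such safeguard.

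The severity rule creates a new record for improvement as well as worsening, and the timing-only definition cannot tell the two apart. Depending on which start date the new record carries, either improvements are counted as emergent or worsening of pre-dose events is missed. At stake is what the period TEAE tables mean: whether a count refers to events that arose or worsened in that period.

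**Working it through.** **A. Partial start dates.** The documents state no figure to reproduce, so the rule is applied to made-up records.

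- Start March 2021, stop 5 March, first dose 20 March. The month matches, so the start becomes 20 March, which is 20 − 5 = 15 days after the stop.
- Start 2021, stop June 2021, first dose 15 July 2021. The start becomes 15 July. The SAP's own end-date rule sets the stop to 30 June (unless last contact was earlier), again 15 days before the start.
- Start completely missing, stop 5 March, first dose 20 March. The rule makes this a TEAE only if the stop is on or after first dose, so it does not. Knowing less about the start gives the better answer.

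*Reach.* Assume that first doses are spread evenly over a year and event starts evenly over a screening period of L days (the protocol gives 2 to 4 weeks). Among events that truly began in screening, the share beginning in the calendar month of first dose is 1 − (L + 1)/(2 × 365/12). For the calendar year it is 1 − (L + 1)/(2 × 365).

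| L (days) | Month and year known | Year only known |
|---|---|---|
| 14 | 1 − 15/60.8 = 75% | 1 − 15/730 = 98% |
| 21 | 1 − 22/60.8 = 64% | 1 − 22/730 = 97% |
| 28 | 1 − 29/60.8 = 52% | 1 − 29/730 = 96% |

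These are shares of partially dated screening events that would be moved to first dose. They are not error rates: the result is clearly wrong only for the subset with a stop known to precede first dose.

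The rule does not push events into the Maintenance Period, because it refers only to the first study dose. With first dose on 20 March 2021, Week 16 falls 112 days later, on 10 July. A start of July 2021 becomes 1 July, in the Initial Period.

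**B. Severity changes.** First dose is 20 March. For the Week 16 rows, assume that events are assigned to periods by the start date of the record.

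| Event | New record dated at the change | New record keeps first onset date |
|---|---|---|
| Moderate headache 10 March, mild from 21 March | TEAE, though it improved | Not a TEAE |
| Mild headache 10 March, severe from 21 March | TEAE, correctly | Not a TEAE; worsening lost |
| Moderate before Week 16, mild after | Enters the Maintenance table | Stays in Initial |
| Mild before Week 16, severe after | Enters the Maintenance table, correctly | Worsening missing from Maintenance |

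Each reading gets half the cases wrong. Counting a subject once per event (Protocol 10.1.4.2) does not help, because the earlier record is pre-treatment or in another period's table.

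**C. Size.** The plan expects 190 re-randomised nemolizumab subjects. Its assumptions give 750 × 2/3 = 500, and 500 × 0.85 × 0.45 = 191, which agrees closely. Per arm: 190/3 = 63.3. One subject with a re-entered event moves an arm's incidence by 1/63.3 = 1.6 points, and three by 3/63.3 = 4.7 points. If C subjects in all have such a record, and severity changes are equally likely in each arm, 1:1:1 re-randomisation gives C/3 per arm and an expected difference of zero. The 1.6 and 4.7 points therefore illustrate chance imbalance. The documents give no value for C.

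**The case against.** The strongest reply is that the severity mechanism is partly inferred. The protocol says that the change is a separate event but not which start date it takes, and asking for the date of first occurrence could mean the first onset. The period-assignment rule is also unwritten, and CRF completion instructions are not among the documents. This stands: a reader might infer that improvements will certainly be miscounted, but the text does not settle it. It does not clear the plan, because the alternative dating loses worsening. The chronic-disease rule softens that loss for chronic conditions only.

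Second, a reader might infer that nemolizumab events are shifted systematically onto the Q8W or placebo arm. The documents do not support that. All three arms come from the same Q4W responders, so events ongoing at Week 16 are balanced in expectation. Bias would need rates of severity change that differ by arm, and nothing in the documents shows this. In the Initial Period both arms follow the same rules.

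Third, a reader might infer that all safety tables are inflated. An improved record cannot be severe, so the severe-TEAE tables gain nothing. Several AESI categories are limited by content (Protocol 9.2.1.1): easing asthma is not worsening asthma, and much of the infection category requires severity or prolonged treatment. The oedema categories have no severity condition and remain exposed. Exclusion criterion 4 also removes most infections that could straddle first dose. The planned overall-study tables do not count the same subject and term again across Week 16.

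Fourth, where the stop date does not settle the matter, moving a partial start to first dose is a sensible cautious default. That stands.

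**Conclusion.** The partial-date rule is wrong as written for one narrow group: events with an incomplete start in the month or year of first dose and a stop known to precede it. For these it produces an impossible date order and an unwarranted TEAE. It does not reclassify fully dated pre-treatment events.

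The severity gap is real but conditional. With no dating rule and no worsening criterion, the TEAE tables either take in improvements or drop worsening of pre-dose events. If records are dated at the change and assigned to periods by start date, the expected effect is a modest, non-differential inflation of period TEAE incidence. That rests on severity changes occurring at similar rates across arms. It is not a demonstrated bias between arms, and its size cannot be derived, because neither the frequency of severity changes nor that of partial dates is given.

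**What to change.** **SAP 8.3.** Add that an imputed adverse-event start may not be later than the known stop date, and that an event whose stop date, or the known part of it, precedes first dose is pre-treatment. Keep the present default otherwise. This is one sentence and costs nothing.

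**SAP 13.1.** State that a severity-change record is dated at the change. Count it as emergent in a period only if the event is new in that period or its severity exceeds that at the start of the period (first dose or re-randomisation). State how events are assigned to periods.

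No new data collection is needed. The cost is a small derivation linking records of the same event, with blinded review of a few cases. The drawback is that linking by preferred term and contiguous dates could merge distinct episodes, which is why that review is needed.
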